2 SCHEDULE OF ASSESSMENTS

Table 2 is a schedule of assessments to be performed during the study. **Table 3** outlines detailed sampling times for pharmacokinetic (PK), urine and blood plasma cell-free DNA (cfDNA), and other laboratory parameters. All data obtained from these assessments must be supported in the subject's source documentation.

Molecular prescreening for susceptible fibroblast growth factor receptor 3 (FGFR3) genetic alterations (mutations, and gene fusions or rearrangements; hereafter referred to collectively as "FGFR3 alterations") testing can be conducted any time before the Screening visit.

All baseline/screening assessments, including screening cystoscopy (for subjects with a bladder) and imaging assessments must be conducted within 28 days before randomization. Baseline scans must be sent for blinded independent central review (BICR) to confirm absence of residual or metastatic disease before randomization. In the event that subjects have a baseline/screening laboratory assessment that excludes them from the study, the baseline/screening laboratory assessment can be repeated to re-check their eligibility.

Whenever feasible, vaccinations should be administered at least 30 days prior to randomization.

Baseline/Screening assessments that are conducted within 3 days before the first treatment can be used to satisfy the Day 1 requirement. Every effort must be made to follow the schedule outlined.

Unless otherwise indicated, for Treatment Period there is a minus-3-day window on assessments (study visits on C1D1, C1D4, C1D7, C1D14 and C2D1) or a minus-5-day window (study visits on C4D1, C7D1, C10D1, and C13D1) on assessments to take into account scheduling over weekends and holidays. For study visits on Day 21 of all cycles (C1 to C13) there is a minus-2-day window. For postbaseline imaging assessments, a ± 7 -day window is allowed, except for the first postbaseline assessment ($+7$ -day window permitted). The end of treatment (EOT) visit is to be conducted no later than 5 days from the decision to discontinue study drug.

For visits that occur every 6 months after the EOT or the End of Study (EOS) visit, a ± 7 -day window is allowed. For Survival Follow-up visits that occur annually after EOT or the EOS, a ± 14 -day window is allowed (see Section 9.9 for details on long-term overall survival [OS] follow-up after the EOS).

Table 2: Schedule of Assessments

Assessment	Molecular Prescreening ^b	Screening ^b	Treatment Period Clinic Visits (Cycle and Day) ^a							30-Day Post-Treatment Follow-Up	Every 6 Months after EOT ^c and at EOS	Survival Follow-Up ^d
			C1 D1	C2 D1	C4 D1	C7 D1	C10 D1	C13 D1	C13 D28 or EOT ^c			
Visit Window (days) ^e		-28 to -1	-3	-3	-5	-5	-5	-5	±5	±5	±7	±14
Informed consent for molecular prescreening	X											
Prescreening FGFR3 alteration testing by F1CDx ^b	X											
FGFR3 alteration documentation		X										
PD-L1 testing ^f			X ^f									
Informed consent ^g		X										
Inclusion/exclusion criteria ^g		X										
Demographics		X										
ECOG performance status		X	X	X	X	X	X	X	X			
Medical history		X										
Diagnosis & extent of cancer		X										
Prior medication and antineoplastic therapy		X										
Ophthalmic assessment ^h		X		X	X	X	X	X	X			
Physical examination ⁱ		X	X	X	X	X	X	X	X		X	
Weight and BMI (height at screening only)		X	X	X	X	X	X	X	X			X
Vital signs		X	X	X	X	X	X	X	X			X
12-Lead ECG ^j		X	X	X						X		
QOL assessment ^k			X	X	X	X	X	X	X		X ^k	
Blood samples:												
Hematology ^{l,m}		X		Refer to Table 3 for specific schedule					X			
Clinical chemistry ^{l,m}		X		Refer to Table 3 for specific schedule					X			
Coagulation		X		As clinically indicated								
Pharmacokinetics				Refer to Table 3 for specific schedule								
cfDNA				Refer to Table 3 for specific schedule ⁿ						X ⁿ		

Assessment	Molecular Prescreening ^b	Screening ^b	Treatment Period Clinic Visits (Cycle and Day) ^a							30-Day Post-Treatment Follow-Up	Every 6 Months after EOT ^c and at EOS	Survival Follow-Up ^d
			C1 D1	C2 D1	C4 D1	C7 D1	C10 D1	C13 D1	C13 D28 or EOT ^c			
Visit Window (days) ^e	-28 to -1	-3	-3	-5	-5	-5	-5	-5	±5	±5	±7	±14
Urine samples:												
Urinalysis		X (subjects with a bladder)	As clinically indicated (all subjects)									
Cytology		X		X	X	X	X	X	X		X	
cfDNA			Refer to Table 3 for specific schedule ⁿ								X	
Pregnancy test in WOCBP ^o		X	Monthly (refer to Table 3 for schedule)							X		
Chest, Abd/Pelvis CT or MRI scan ^p		X		X	X	X	X	X	X		X (every 3M) ^p	
Cystoscopy (subjects with a bladder) ^q		X		X	X	X	X	X	X		X	
Randomization ^r		X										
Administer study drug (3 weeks on [Days 1-21] /1 week off [Days 22-28] ^s			X									
AEs		X ^t	X (Refer to Table 3 for additional schedule)							X	X	
Concomitant medications			X (Refer to Table 3 for additional schedule)							X	X	
Antineoplastic therapies since discontinuation of study treatment											X	X
Newly obtained tumor sample (if medically feasible)				Collect upon any disease recurrence ^u								
Survival follow up ^d											X	X

Abbreviations: Abd=abdomen; AE=adverse event; BICR=blinded independent central review; BMI=body mass index; C=cycle; cfDNA=cell-free DNA; CRF=case report form; CT=computed tomography; D=day; DFS=disease-free survival; ECG=electrocardiogram; ECOG=Eastern Cooperative Oncology Group; EDC=electronic data capture; EORTC=European Organization for Research and Treatment of Cancer; EOS=end of study; EOT=end of treatment; EQ-5D-5L=EuroQOL 5 dimensions, 5 levels questionnaire; F1CDx=FoundationOne CDx test (from Foundation Medicine USA); FGFR3=fibroblast growth factor receptor 3; ICF=informed consent form; M=months; MRI=magnetic resonance imaging; OCT=optical coherence tomography; OS=overall survival; PD-L1=programmed death-ligand 1; PK=pharmacokinetics; QLQ-Core 30=Quality Of Life Questionnaire Core 30; QOL=quality of life; UTUC=upper tract urothelial carcinoma; SAE=serious adverse event; WOCBP=women of childbearing potential.

^a Additional assessments, including sample collection for clinical laboratory assessments, PK and blood and urine cfDNA assessments, pregnancy testing, and collection of AEs and concomitant medications will be as detailed in [Table 3](#).

- b Molecular Prescreening: If F1CDx data are not available from testing that occurred as part of the subject's standard of care, molecular prescreening assessments can be done (after signing Molecular Prescreening ICF) any time before the initiation of the Screening visit. Further details are provided in Section 9.1.
Screening: All baseline/screening assessments, including baseline imaging assessments and screening cystoscopy (for subjects with a bladder) must be conducted within 28 days before randomization. Baseline/screening assessments that are conducted within 3 days before the first treatment can be used to satisfy the C1D1 requirement. Every effort must be made to follow the schedule outlined.
- c After EOT, subjects will be followed up every 6 months until metastatic recurrence by BICR or metastatic recurrence by investigator assessment if local/regional or contralateral invasive recurrence by BICR has already occurred. The EOT visit should be no later than 5 days after treatment discontinuation. See footnote p regarding schedule of imaging assessments.
- d After metastatic recurrence by BICR or metastatic recurrence by investigator assessment if local/regional or contralateral invasive recurrence by BICR has already occurred, subjects will be followed up for survival every 6 months for 1 year, then annually thereafter (via phone or office visit) for 1 year after the final DFS event goal is reached (ie, EOS). See Section 9.9 for details on long-term OS follow-up (under a separate protocol).
- e C1D1 has a minus-3-day window to account for scheduling over weekends and holidays. During study treatment, there is a minus-3-day window on C2D1 assessments and a minus-5-day window on C4D1, C7D1, C10D1, and C13D1 assessments to take into account scheduling over weekends and holidays, if not explicitly specified otherwise. For postbaseline imaging assessments, a \pm 7-day window is allowed, except for the first postbaseline assessment (+7-day window is permitted).
- f If local PD-L1 test has been completed and status is available, enter the status information in EDC. If local PD-L1 is not already known, PD L1 testing can be initiated at C1D1 or at any time after the subject is deemed eligible. See Section 10.3 for additional details for PD-L1 testing.
- g Written informed consent is required before performing any study-specific tests or procedures and may be obtained at any time before such test or procedure. Results of standard-of-care tests or examinations and review of inclusion/exclusion criteria performed before obtaining informed consent and within 28 days before randomization may be used for screening assessments rather than repeating such tests. If the subject did not receive platinum-based chemotherapy in the perioperative setting (see inclusion criterion #4, Section 6.1), the reason must be documented in the CRF.
- h Ophthalmic assessment (performed by an ophthalmologist) will also be done as clinically indicated. Ophthalmic assessment includes visual acuity testing (including corrected distance acuity), slit lamp examination of the anterior eye segment, intraocular pressure, retinal OCT, and dilated fundoscopy. Additional examination methods such as specular microscopy and corneal pachymetry will be done as clinically indicated. Retinal OCT scans will be read locally and images will be provided to the OCT imaging vendor. Refer to the Study Manual for details regarding image collection and transfer or shipment. Ophthalmic assessment will be conducted at C13D28 or EOT visit unless performed within previous 4 weeks.
- i Full physical examination at screening, C1D1, and C13D28/EOT; abbreviated or symptom-directed physical examination at C2D1, C4D1, C7D1, C10D1, C13D1, every 6 months after EOT, and at the EOS visit.
- j For each subject, 12-lead ECGs will be done at Screening; predose on Day 1 of Cycles 1 and 2; and at C13D28 or EOT visit.
- k QOL assessments should be conducted before study drug administration, AE evaluation, and disease status notification, and preferably in order of EQ-5D-5L then EORTC QLQ-C30. Subjects should complete QOL assessments for 18 months; for subjects who complete all 52 weeks of study drug treatment, the last assessment will be at the first 6-month follow-up visit after discontinuation of study drug. Assessments do not need to be administered at the EOT visit if they were completed within the previous 7 days at a regularly scheduled visit.
- l Laboratory tests will be collected and analyzed on the scheduled day, even if study drug treatment is being withheld. Laboratory tests must be conducted within the windows specified in the protocol.
- m Hematology will be assessed at C1D1, C2D21, C4D21, C7D21, C10D21, C13D21, and C13D28 or EOT (refer to [Table 3](#)). Clinical chemistry will be assessed at C1D1, C1D4, C1D7, C1D14, C1D21; Cycles 2-13 (Day 21); and C13D28 or EOT (refer to [Table 3](#)).

The schedules for these clinical laboratory tests coincide, as closely as possible, with the blood draws specified for PK and cfDNA (refer to [Table 3](#)). Every attempt should be made to collect the clinical chemistry sample at the same time as the PK sample taken at 4 hours after study drug administration.

- ⁿ At the time of local/regional or contralateral invasive or metastatic recurrence, a blood and urine sample will be collected for analysis of cfDNA.
- ^o Serum or urine pregnancy test within 7 days before the first dose of study drug; thereafter, pregnancy tests should be conducted monthly (at study visit on Day 21 of each cycle [per [Table 3](#)]) and may be serum or urine based on standard at the institution. Where required while the subject is receiving study drug, more frequent urine pregnancy tests may be conducted.
- ^p Baseline CT/MRI scans must be performed within 28 days before randomization and must be submitted for BICR to confirm absence of residual or metastatic disease before randomization. For an individual subject, whichever modality (CT or MRI) is used at screening, that same modality should be used for radiographic assessment throughout the study. Refer to the Study Manual for details regarding image collection and transfer or shipment. For postbaseline imaging assessments, a ± 7 -day window is allowed, except for the first postbaseline assessment ($+7$ -day window permitted). Perform CT/MRI scans every 3 months for a total of 24 months since start of treatment, then annually until metastatic recurrence by BICR or metastatic recurrence by investigator assessment if local/regional or contralateral invasive recurrence by BICR has already occurred. Subjects who discontinue study drug for reasons other than metastatic recurrence by BICR (as stated in the previous sentence) will continue to have radiographic assessments every 3 months for a total of 24 months since start of treatment, then annually until metastatic recurrence by BICR or metastatic recurrence by investigator assessment if local/regional or contralateral invasive recurrence by BICR has already occurred. A radiographic assessment should be conducted at the EOT visit, unless taken within the previous 4 weeks. CT/MRI scans indicating unequivocal recurrence (as defined in [Table 8](#)) must be read locally and submitted for BICR as well as any supporting report (including pathology and cytology reports) if a biopsy was conducted at the time of recurrence. Refer to the Study Manual for details regarding image collection and transfer or shipment.
- ^q Perform cystoscopy (for UTUC subjects with a bladder) at Screening, within 28 days before randomization, and at C4D1, C7D1, C10D1, C13D1, and C13D28 or EOT, and then every 6 months for a total of 24 months since start of treatment; then annually until metastatic recurrence by BICR or metastatic recurrence by investigator assessment if local/regional or contralateral invasive recurrence by BICR has already occurred. Subjects who discontinue study drug for reasons other than recurrence (as stated in the previous sentence) will continue to have cystoscopy/cytology as described until metastatic recurrence by BICR or metastatic recurrence by investigator assessment if local/regional or contralateral invasive recurrence by BICR has already occurred. Conduct cystoscopy/cytology at the EOT visit, unless done within the previous 4 weeks.
- ^r Randomization will occur after the subject completes the Screening visit and is deemed eligible for study (including documented medical monitor approval) and before C1D1. Treatment starts within 1 week of randomization. Note: only under certain unforeseen circumstances that are not caused by noncompliance or inappropriate planning [eg, adverse weather], randomization may occur after day 120 from definitive surgery but window for randomization and dosing should be 127 days total (120 days $+7$ days).
- ^s Study drug may be dispensed at study visits on Day 1 of C1, C2, C4, C7, C10, and C13 and/or monthly at study visits per local standard practice.
- ^t Only report protocol-mandated procedure-related AEs. See Sections [10.5.1.3](#) and [10.5.1.4](#) for details on collection and reporting of AEs and SAEs.
- ^u Histologic/cytologic confirmation is the preferred criterion to determine unequivocal recurrence, and new lesions should be biopsied to confirm recurrence when safe and feasible. All CT/MRI scans and biopsy reports (including pathology and cytology reports) must be submitted for BICR assessment.

Table 3: Schedule of Assessments: Pharmacokinetic and Blood and Urine cfDNA Sample Collection, Laboratory Parameters, and Adverse Event and Concomitant Medication Assessments

Cycle	Day	Parameters						
		PK ^a		cfDNA ^a	Blood and Urine (predose)	Clinical Chemistry ^b	Hematology ^b	Pregnancy Test ^c
		Predose (hrs before dose)	Postdose (hrs ±30 min)					
1	1	0	4	X	X	X		X
1	4				X			
1	7				X			
1	14				X			
1	21 ^d	0	4	X	X		X	X
2	21 ^d	0	4		X	X	X	X
3	21 ^d	0	4	X	X		X	X
4	21 ^d	0	4		X	X	X	X
5	21 ^d	0	4	X	X		X	X
6	21 ^d	0	4		X		X	X
7	21 ^d	0	4	X	X	X	X	X
8	21 ^d	0	4		X		X	X
9	21 ^d	0	4	X	X		X	X
10	21 ^d	0	4		X	X	X	X
11	21 ^d	0	4	X	X		X	X
12	21 ^d	0	4		X		X	X
13	21 ^d	0	4	X	X	X	X	X
13	28(or EOT) ^e	If within 24 hrs of last dose	NA	If not done within 28 days prior	X	X	X	X

Abbreviations: AEs=adverse events; C=cycle; cfDNA=cell-free DNA; Conmeds=concomitant medications; D=day; eCRF=electronic case report form; EOT=end of treatment; hrs=hours; NA=not applicable; PK=pharmacokinetic(s).

NOTE 1: On the days of PK and cfDNA sampling, subjects should not take their study drug dose at home; subjects should take their study drug with them to the study center where dosing will be supervised and administration time recorded.

NOTE 2: If a subject is not on study drug, then no PK or cfDNA sample will be collected. PK and cfDNA sampling will resume once the subject is back on study drug.

^a On PK sampling days after C1D1, the time of the last study drug dose (ie, time of infigratinib/placebo administration on the previous day) before the predose PK sample will be recorded in the eCRF. For any subject who permanently discontinues study drug, attempts should be made to collect PK and blood (2 tubes, 16-20 mL) and urine cfDNA samples from the subject at the time of discontinuation, if the samples can be collected within 24 hours of last dose.

^b Samples for clinical laboratory tests (including hematology, clinical chemistry, and pregnancy) will be collected and analyzed on the scheduled day even if study drug is being withheld; where applicable, every attempt should be made to collect samples for clinical laboratory tests on the same day as PK and cfDNA sample collection (window is minus-3 days for C1D1, C1D4, C1D7, and C1D14). Every attempt should be made to collect the clinical chemistry sample at the same time as the PK sample taken at 4-hours after study drug administration.

^c Pregnancy test may be serum or urine based on standard at the institution. Where required while the subject is receiving study drug, more frequent urine pregnancy tests may be conducted.

^d A minus-2-day window before Day 21 is allowed (specifically on Days 19, 20, or 21).

^e Blood (2 tubes, 16-20 mL) and urine cfDNA samples will be collected at C13D28 or EOT if not done within 28 days before. At the time of local/regional or contralateral invasive or metastatic recurrence, blood (2 tubes, 16-20 mL) and urine samples will be collected for analysis of cfDNA. Sample for PK to be collected if within 24 hours of last dose of study drug.

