7.2 Information on Dosing with Study Drug

7.2.1 *Subject Instructions for Dosing*

Subjects with mild or moderate renal impairment (creatinine clearance 30 mL/min to ≤ 89 mL/min) should be administered a starting dose of 100 mg QD infigratinib on a 3 week on (21 day)/1 week off (7 day) schedule. Subjects with mild (total bilirubin $>$ ULN to $1.5 \times$ ULN or AST $>$ ULN) and moderate hepatic impairment (total bilirubin $>$ 1.5 to $3 \times$ ULN with any AST) should be administered a starting dose of 100 and 75 mg QD of infigratinib, respectively, on a 3 weeks on (21 day)/1 week off (7 day) schedule. For subjects with combined hepatic and renal impairment, the lower of the 2 starting doses should be administered.

Subjects should be instructed to take the daily dose of study drug in the morning, at approximately the same time each day (24 \pm 4-hour interval). Subjects will take their first dose of study drug at the study center on Cycle 1 Day 1 (C1D1). On the days of PK sampling, subjects should not take their study drug dose at home; subjects should bring their study drug with them to the study center where dosing of study drug will be supervised and administration time recorded. Administration may fall outside of the \pm 4-hour interval on the days of PK sampling. On PK sampling days after C1D1, the time of the last study drug dose (ie, time of study drug administration on the previous day) before the predose PK sample will be recorded in the eCRF.

Study drug should be taken in the fasted state at least 1 hour before or 2 hours after a meal. It should be taken with a large glass of water (\sim 250 mL) and consumed over as short a time as possible. Subjects should be instructed to swallow the capsules whole and not chew them.

If the subject forgets to take the scheduled dose of study drug in the morning (other than on a day of PK sampling), he/she should not take the dose more than 4 hours after the usual time and should continue treatment the next day. Any such doses that are missed should be skipped altogether and should not be replaced or made up at the next scheduled dosing.

If vomiting occurs following dosing with study drug, re-dosing is not permitted the same day. Dosing should resume the next day. If vomiting occurs on a PK sampling day within the first

4 hours postdosing, this event is to be noted on the Dose Administration page of the eCRF, as well as on the AE page, as appropriate.

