7.5 Supportive Care Guidelines

Any supportive care for disease related symptoms, including any medication or therapy for a concurrent medical condition are permitted, except if specifically prohibited below.

7.5.1 *Hematopoietic Growth Factors*

Hematopoietic growth factors (eg, erythropoietin [EPO], granulocyte colony-stimulating factor (G-CSF), granulocyte-macrophage colony-stimulating factor [GM-CSF]) and blood transfusions are not to be administered prophylactically or to be used to meet eligibility criteria. However, these drugs may be administered according to the label of these agents or as dictated by local practice or guidelines established by the American Society of Clinical Oncology (ASCO), European Society of Medical Oncology (ESMO), or other appropriate regional societies.

7.5.2 *Management of Hyperphosphatemia*

Hyperphosphatemia is a recognized on-target effect of potent and selective inhibitors of the FGFR pathway. While on study drug, subjects should avoid foods that are especially high in phosphate and, if possible, should restrict dietary phosphate to 600 – 800 mg/day. High-phosphate foods include dairy products; meats, nuts, and other high-protein foods; processed foods; and dark colas. Phosphorus will be checked at screening and starting on Cycle 1 Day 4. Subjects who experienced hyperphosphatemia should take a phosphate binder such as sevelamer, sacroferric oxyhydroxide, lanthanum carbonate, ferric citrate, etc. within 30 minutes of a meal on the day while taking study drug. Once the subject has had hyperphosphatemia, the subject should

remain on a low phosphate diet, if possible, and take phosphate binder on the days study drug is taken even, if the serum phosphorus is normalized. Unless otherwise specified by the local prescribing information or institutional practice, the following regimen should be used to manage hyperphosphatemia:

- For serum phosphorus $>5.5 - \leq 7.5$ mg/dL
 - Start sevelamer 800 mg 3-times per day with meals
 - Increase the dose of sevelamer up to 1200 mg every 8 hours
- For serum phosphorus >7.5 mg/dL
 - Increase the dose of sevelamer up to 1600 mg (2 tablets per meal) every 8 hours
 - Consider adding acetazolamide, 2 to 3 tablets (250 mg) per day

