- Newly obtained tumor sample (if medically feasible) upon any recurrence. Biopsy reports, including pathology and cytology, must be submitted for BICR, as well as imaging (CT/MRI scans) assessments. Refer to the Study Manual for details regarding report collection and transfer or shipment. With subject consent, tumor samples collected upon local/regional or contralateral invasive or metastatic recurrence as part of standard of care may be provided to the sponsor for exploratory objectives related to biomarkers of urothelial carcinoma biology and the potential association of biomarkers with efficacy, disease recurrence, and resistance to study medications.

9.7 30-day Post-treatment Follow-up (± 5 Days)

All subjects must complete safety follow-up assessments 30 days after the last dose of the study drug, as outlined in [Table 2](#).

Information relating to anticancer therapies taken since discontinuation of study drug and AEs (including concomitant medication taken for ongoing AEs) will be collected for 30 days after the last dose of the study drug.

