Disease-free survival time is calculated as the number of months from randomization to the date of local/regional invasive or metastatic recurrence or death due to any cause (referred as DFS event) ((date of DFS event - date of randomization + 1)/ (365.25/12)). Subjects without recurrence (local/regional invasive or metastatic) or death will be censored at the last radiology assessment if previous cystoscopy result within 6 months is negative for muscle invasive disease, otherwise, DFS will be censored at the last complete recurrence assessment. Subjects who have no disease assessments after baseline will be censored on the randomization date. The primary DFS endpoint will be based on the central review (BICR), while for the secondary endpoint, the investigator reviewed DFS will be based on investigator review.

DFS including intraluminal low risk recurrence

The investigator reviewed DFS including intraluminal low risk recurrence is defined as the time from randomization to any recurrence as determined by investigator, or death due to any cause, whichever occurs earlier. For subjects without documented recurrence and are still alive, they will be censored at the last complete disease assessment (or, if no disease assessments are performed after the baseline visit or no death has been recorded, at the time of randomization).

Relative dose intensity

The relative dose intensity is defined as cumulative actual dose a subject have received divided by the planned cumulative dose. For example, a subject takes study drug from Day 1 to Day 21 at 125 mg/day; then from Day 29 to Day 30 at 100 mg/day, and end treatment afterward. The cumulative actual dose $=(21*125)+(100*2)=2825$ mg; the planned cumulative dose $=(21*125)+(125*2)=2875$ mg. The relative dose intensity $= 2825/2875=98.3\%$.

Study Day 1

Study Day 1 is defined as the day of the first administration of study treatment after randomization.

Treatment Duration

Treatment duration is defined as last dose date – first dose date +1.

On Treatment Period

On treatment period is defined as first administration of study treatment through 30 days after the last administration of study treatment inclusively.

Treatment-emergent Adverse Event

A treatment-emergent adverse event is defined as an adverse event that occurs on or after the first administration of study treatment and within 30 days after the last administration of study treatment.

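### The Day 4 chemistry may be drawn on Day 1, and the 30-day safety visit may be held before the adverse event period it serves has ended.

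*Protocol*

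**What the plan says.** **Early chemistry.** Protocol Table 2, footnote m, gives the schedule: "Clinical chemistry will be assessed at C1D1, C1D4, C1D7, C1D14, C1D21; Cycles 2-13 (Day 21); and C13D28 or EOT". The first dose is fixed in Section 7.2.1: "Subjects will take their first dose of study drug at the study center on Cycle 1 Day 1 (C1D1". Section 7.5.2 describes the phosphorus monitoring: "Phosphorus will be checked at screening and starting on Cycle 1 Day 4". The text ahead of Table 2 sets the window: "there is a minus-3-day window on assessments (study visits on C1D1, C1D4, C1D7, C1D14 and C2D1". Table 3, footnote b, repeats it for laboratory samples: "window is minus-3 days for C1D1, C1D4, C1D7, and C1D14". The stated purpose is "on assessments to take into account scheduling over weekends and holidays", and sites are asked to make every effort to keep to the schedule. Table 2, footnote l, asks for laboratory tests on the scheduled day, but also requires them to fall within the protocol's windows.

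**Adverse events after treatment.** Section 9.7 says that adverse event information "will be collected for 30 days after the last dose of the study drug". Sections 7.2.5.2 and 10.5.1.3 set the same 30-day period. SAP Section 6 counts an event as treatment-emergent if it occurs "within 30 days after the last administration of study treatment". Protocol Section 11.3.8.2 and SAP Section 8.10.1 agree. The visit that closes this period has a window of plus or minus 5 days (Table 2 and the title of Section 9.7). The assessments listed in Section 9.8 for later visits do not include adverse events.

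**The concern.** In each case a window allows the assessment to take place before the thing it is meant to observe.

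A Day 4 chemistry taken on Day 1 reflects one dose or none, so it adds little to the Day 1 draw as a first look at phosphate on treatment. Section 7.5.2 and Table 6 tie actions to phosphate values, and hyperphosphatemia was the most common adverse event in the Phase 1 study (65.4%, Section 3.4.2). Values filed under the Day 4 label could also mix exposed and unexposed samples.

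A safety visit held before Day 30 leaves part of the treatment-emergent period with no clearly scheduled occasion to ask about new events. Reported rates would then depend partly on when each visit happened to fall.

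**Working it through.** The plan states no figure to reproduce. The check is day arithmetic on the windows, and it does not depend on sample size, events or alpha.

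**1. Chemistry.** The windows come from Protocol Section 2 and Table 3 (footnotes b and d).

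| Draw | Window | Allowed days |
|---|---|---|
| C1D4 | minus 3 | 4 − 3 = 1, so Days 1 to 4 |
| C1D7 | minus 3 | 7 − 3 = 4, so Days 4 to 7 |
| C1D14 | minus 3 | 14 − 3 = 11, so Days 11 to 14 |
| C1D21 | minus 2 | 21 − 2 = 19, so Days 19 to 21 |

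- Day 1 lies inside the C1D4 range. It is the first dosing day and has its own chemistry draw. No text sets a minimum gap between the two samples.
- If C1D4 is drawn on Day 1, the next scheduled chemistry is C1D7, on Day 4 at the earliest and Day 7 at the latest.
- The greatest delay to the first check after Day 1 is therefore 7 − 4 = 3 days.
- If every window is used in full, the three draws fall on Days 1, 4 and 11, and a Day 4 value still exists.

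**2. The 30-day visit.** The anchor is the last dose (Section 9.7).

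- Allowed range: 30 − 5 = 25 to 30 + 5 = 35, so Days 25 to 35.
- A visit on Day v before Day 30 leaves 30 − v days of the collection period still to run. The maximum is 30 − 25 = 5 days (Days 26 to 30), or 5/30 = 16.7% of the period.
- A visit on Days 30 to 35 leaves none.

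**3. Are those days covered by something else?**

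- Serious events through 30 days after the last dose must be reported within 24 hours of the site learning of them (Section 10.5.1.4), whatever the visit date.
- Section 7.2.5.2 requires weekly follow-up for 4 weeks, but only when study drug was interrupted or stopped for an adverse event or a clinically significant laboratory value.
- Section 10.5.1.6 concerns events already detected.
- For a subject outside these cases, no passage clearly schedules a contact that would bring out a new non-serious event after an early visit.

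**4. Effect on the analysis.** SAP Section 6 defines baseline as the last measurement before the first dose. A sample labelled C1D4 but drawn before dosing on Day 1 meets that definition. SAP Section 8.10.4 summarises chemistry at selected visits and by post-baseline maximum and minimum, and does not say whether values are placed by visit label or by actual day.

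**The case against.** The strongest reply has four parts.

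*The windows are limited.* They exist for weekends and holidays, sites must try to keep to the schedule, and laboratory tests belong on the scheduled day. This makes a Day 1 draw less likely but does not rule it out. The footnote that mentions the scheduled day also makes the windows binding for laboratory tests, and a Day 4 falling on a weekend is just when a site would use the window.

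*Neither check is lost.* This stands. A reader might infer that the windows defeat the safety checks, but the Day 7 draw cannot precede Day 4. A reader might also infer that 17% of the post-treatment days have no adverse event collection. The documents say otherwise: Sections 7.2.5.2, 9.7 and 10.5.1.3 require collection for the full 30 days regardless of the visit date, and an early visit does not alter the treatment-emergent definition. What may be absent is a scheduled contact.

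*The clinical stake is not shown.* This also stands. The 65.4% is an all-grade rate over the whole Phase 1 study, across doses and schedules, and is not an early-onset rate. The nearest timing figure is a median of about 22 days to first dose interruption before prophylactic phosphate-lowering therapy (Section 3.4). Nothing in the documents measures the cost of a first check on Day 7 instead of Day 4.

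*Table 2 might schedule later adverse event collection.* In the copy reviewed, its columns are displaced: the end-of-treatment ECG mark sits under the 30-day column, against footnote j. Its adverse event row can neither confirm nor exclude collection at the six-monthly visits. Even if it did confirm it, events from Days 26 to 30 would be asked about months later.

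**Conclusion.** The point holds as two mismatches between a window and a stated purpose.

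- The C1D4 chemistry may coincide with the C1D1 draw. The first check after Day 1 can then slip by up to 3 days, to Day 7 at the latest.
- The 30-day visit may precede the end of the adverse event period by up to 5 days. Non-serious events in that interval may be missed or ascertained late, although their collection is still required.

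This assumes that sites may use the windows as written and that the Study Manual and Laboratory Manual, which are not available here, do not narrow them or add a contact. How often either window was used in full is unknown, so no effect on adverse event rates can be calculated.

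The priority is low: a cheap improvement. SAP Section 1 records that the study was closed early, so changed windows would alter monitoring for few or no subjects. The dating of chemistry values still matters for the abbreviated report.

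**What to change.** - Reconcile the Section 2 window text, Table 2 (footnotes l and m), Table 3 (footnote b) and Section 7.5.2 so that the C1D4 sample cannot coincide with the C1D1 draw.
- Reconcile the visit window in Table 2 and Section 9.7 with the 30-day period in Sections 7.2.5.2 and 10.5.1.3 and SAP Section 6, so that adverse event ascertainment reaches the end of that period.
- The sponsor chooses the windows; none is proposed here.
- In SAP Section 8.10.4, state that early chemistry values are assigned by actual study day relative to the first dose. Report how many 30-day visits took place before Day 30.

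The cost is a few lines of wording, a date-based derivation and one count. The downside is slightly less scheduling freedom for sites.
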